#### Glossary of abbreviations

AE Adverse Event
CF Consent Form
CI Chief Investigator
CRF Case Report Form

CTIMP Clinical Study of Investigational Medicinal Product

CTR Centre for Trials Research

CTU Clinical Trials Unit CU Cardiff University

**GAFREC** Governance Arrangements for NHS Research Ethics Committees

**GCP** Good Clinical Practice

**GDPR** General Data Protection Regulation 2016/679

**GP** General Practitioner

**HB** Health Board

HS Hidradenitis suppurativaHTA Health Technology Assessment

IC Informed consent

IDMC Independent Data Monitoring Committee

IEC Independent Ethics Committee
IMP Investigational Medicinal Product

**ISF** Investigator Site File

MHRA Medicines and Healthcare Products Regulatory Agency

NHS National Health Service
PI Principal Investigator

PIC Participant Identification Centre
PIS Participant Information Sheet

QA Quality Assurance
QC Quality control
QL (QoL) Quality of Life

R&D Research and Development
RCT Randomised Controlled Trial
REC Research Ethics Committee

**RGF** Research Governance Framework for Health and Social Care

SAE Serious Adverse Event

**SOP** Standard Operating Procedure

**SMF** Study Master File

SMG Study Management Group SSC Study Steering Committee

# 1 Amendment History

The following amendments and/or administrative changes have been made to this protocol since the implementation of the first approved version.

Amendment No.	Protocol version no.	Date issued	Summary of changes made since previous version
NS04	2.1	26.03.20	To section 11.2 added: As a result of the COVID-19 crisis, follow-up processes for the participants currently in the THESEUS study need to be updated. Remote follow-ups via telephone, instead of face-face, can be conducted in order to reduce the risks to participants (ie to them contracting/ spreading the COVID-19 virus) by attending follow-up appointments in person.
NS05	3.0	29.06.20	Section 9.1:  Sites who conduct a search of their patient register and identify potentially eligible patients can send these patients the participant information sheet and consent form. Ideally, the recruitment/baseline appointment should be carried out face-face, however, for those patients who are already known to the study team, eligibility and consent and the baseline appointment can be performed remotely, without the need for the patient to attend the hospital clinic. For those patients who are not known to the research team or have not been reviewed before in person by the study team (the only exceptions

are patients with skin involvement limited to non-intimate sites such as the axilla who could be assessed remotely), they will need to attend a clinic in person to ensure eligibility and assess disease severity.

Community recruitment will occur by publicity involving clinic posters and website adverts on the THESEUS study and HS Trust web sites. The websites will have contact details for a research team member at each participating site. A patient interested in taking part in the study will be asked to contact the participating site directly via these contact details.

Remote recruitment means either by telephone call (plus option to upload photographs of lesions) or video call. Many Trusts are currently consulting with their patients via such remote methods and these can continue to be used in this study.

#### Section 9.4:

Where the recruitment appointment is conducted remotely, the participant will be sent the PIS and consent forms (carbon triplicate copies) via post or email. One copy of the signed consent form will be kept by the participant and the other copies returned to the research site and the CTR.

#### Section 11.2:

As a result of the COVID-19 crisis, follow-up processes for the participants currently in the THESEUS study need to be updated. Remote

	follow-ups via by telephone call (plus option to upload photographs of lesions) or video call instead of face-face, can be conducted in order to reduce the risks to participants (ie to them contracting/ spreading the COVID-19 virus) by attending follow-up appointments in person.
NSA08	Due to COVID-19, the current process of obtaining consent from participants to take part in an interview will be burdensome to the participant and to the research team. This amendment will allow for consent to be taken verbally over the telephone. Verbal consent will be recorded. Interviews will be conducted over the telephone; face-face interviews will no longer be an option.
NSA11	Section 12.1: Clarifications around what constitutes a withdrawal. If the participant wishes to switch to another THESEUS intervention or, if necessary, a non-THESEUS HS intervention, then this would not be classed as a withdrawal.

# 2 Synopsis

Short title	Treatment of Hidradenitis Suppurativa Evaluation Study
Acronym	THESEUS
Internal ref. no.	
Development phase	N/A
Funder and ref.	NIHR HTA (ref 17/98/01)
Study design	Prospective observational cohort study
Study participants	Adults with active Hidradenitis Suppurativa (HS) of any severity
Planned sample size	150
Planned number of sites	10 secondary care sites
Inclusion criteria	
 
Adults at least 18 years old with active HS of any severity
 
Diagnosis meets disease definition (a lifetime history of at least 5 flexural skin boils or 2 flexural skin boils in last 6 months) and confirmed by recruiting clinician with experience of HS care
 
HS not adequately controlled by current treatment
 
At least one of the five study interventions is appropriate for participant's care
 

Exclusion criteria	
 
Unable or unwilling to give informed consent
 
Pregnancy or breastfeeding
 
Not fluent in English (questionnaires are only validated in English)
 

Treatment duration	Up to 6 months
Follow-up duration	12 months
Planned study period	36 months
Primary objective	To inform the design of future HS RCTs and to understand how HS treatments are currently used
Secondary objectives	To determine i) feasibility of recruitment for future RCTs of HS treatments; ii) choice and characterisation of study interventions (dose of medication, type of surgical techniques used); iii) current patient pathways and understanding of what influences patients' and clinicians' treatment choices; iv) choice, feasibility and responsiveness of outcome measure instruments, including evaluation of minimum important difference (MID) to inform sample size calculations; and v) consensus-agreed recommendations for future study designs
Tertiary/Exploratory objectives	N/A
Primary outcomes	Proportion of participants who are eligible, and hypothetically willing, to use the different treatment options

Secondary outcomes	
 
proportion of participants choosing each of the study interventions, with reasons for their choices
 
proportion of participants who switch treatments during the study follow-up period, with reasons for switch
 
treatment fidelity
 
loss to follow-up rates over 12 months
 
efficacy outcome estimates after 6 months' of follow up to inform outcome measure instruments' responsiveness (minimum important difference, MID)
 

Tertiary/Exploratory outcomes	N/A
Intervention	
 
(i) oral doxycycline 200mg OD for 6 months initially;
 
(ii) oral clindamycin and rifampicin both 300mg BD as a combined course for 10 weeks;
 
(iii) laser treatment;
 
(iv) deroofing of sinus tracts;
 
(v) conventional surgery (narrow or wide excision, with a range of closure methods)
 

[figure not shown]

# 3 Study summary & schema

#### 3.1 Participant flow diagram

#### 3.2 Study lay summary

Hidradenitis suppurativa (HS) is a long term, painful skin condition. It involves boils in areas such as the arm pits and groins. It affects young adults of working age. HS has a big effect on quality of life due to pain, scarring and release of pus. It also affects sex and relationships.

Our planned study will provide vital information to answer questions that were identified as priority areas for research by patients with HS and the doctors and nurses who treat them.

#### Aim

To inform the design of future HS trials and to understand how HS treatments are currently used. This involves five steps:

- (1) Describe the treatments used around the country (particularly the type of operation, which can vary from centre to centre);
- (2) See whether patients might consider joining a research study in the future and which treatment(s) they would prefer;
- (3) Define how patients with HS are currently seen within the health service. Learn what influences patients' and clinicians' treatment choices;
- (4) Select the best ways of measuring response to treatment (outcome measures);
- (5) Ask patients and doctors to agree the best design for future HS studies.

#### Design & methods

The HTA wished to fund a study on "Management of HS". We have designed this study in response to the funders. Our team includes people with HS and the leader of a patients' group, skin doctors, general practitioners (GPs), surgeons and research experts. We are supported by a Clinical Trials Unit to make sure that the research is high quality. We are backed by two networks that coordinate skin doctors and plastic surgery doctors around the country.

We have already run surveys of people with HS, skin doctors and surgeons about HS treatment. From these surveys, we have picked five main treatments that future research is likely to want to compare. We will invite people with HS to join the study as volunteers. By inviting people who are treated by skin doctors and those treated by surgeons, we should receive information about a range of treatments. The volunteers will be able to pick from the range of treatments available locally and, for

the year after, we will record what happens to them. We will measure how well the treatment has worked using recommended questionnaires and will help to interpret the questionnaire results by checking what changes in score matter to patients and whether the questionnaires are suitable for normal clinical practice. During the study we will video record the surgical and laser operations to make a training video for future studies.

#### Patient & public involvement

The President of the HS Trust has been a member of our bid team from the beginning and will be part of the group that manages the study. She led our patient survey, using the HS Trust website and social media. The survey, completed by 358 people, helped to shape our study plan. Throughout the THESEUS study, we will interview participants about their study experiences. We will ask about reasons why they might, or might not, take part in future studies. A group of people with HS and doctors/nurses/ researchers involved in the study will meet in a workshop at the end of the study. This will be used to agree the best designs for future HS research.

#### Dissemination

We will present the findings from our study at international meetings of doctors and researchers. We will publish them openly in journals, where anybody can see them. The HS Trust patient support group will host links to these publications on its website, including a plain language summary and podcasts.

# 4 Background

Hidradenitis suppurativa (HS) is a chronic, often painful, inflammatory skin disease that affects approximately 1% of adults (1). It has a large impact on quality of life due to pain, discharge of pus, scarring and effects on sexual function and relationships. Onset is usually in early adulthood and so careers and economic productivity are often affected.

#### Evidence explaining why this research is needed now

Despite being a relatively common condition, the evidence base for management of HS is relatively sparse, as highlighted in the Cochrane review first-authored by the lead applicant (2). Only 12 RCTs with a total of 615 participants were identified. European treatment guidelines are largely based on consensus as a result (3), yet surveys of dermatologists and surgeons conducted by team members have demonstrated idiosyncrasies in treatment strategies by different clinicians, suggesting that there may be undesirable variation in treatment in the UK. To prioritise the large HS research gaps, the lead applicant co-ordinated the HS James Lind Alliance Priority Setting Partnership (PSP), which published a top 10 list of future research priorities including both medical and surgical interventions (4). Our proposal incorporates several HS PSP priorities, including investigation of oral treatments, which was the number one priority, and surgical studies, covered by the sixth and eighth priorities.

Traditionally, there has been a lot of heterogeneity in outcomes across HS studies (5). The funding call from the HTA has come at an opportune time for HS research because core outcome domains have been established by the HIdradenitis SuppuraTiva cORe outcomes set International Collaboration (HISTORIC) (6, 7). The lead applicant is a member of the HISTORIC Steering Committee and so is well-placed to integrate this application with HISTORIC's ongoing work, which involves patients and clinicians in both Europe and North America. Our proposal meets all aspects of the Commissioning Brief by investigating second-line interventions for HS (both medical and surgical) in a prospective cohort study. The cohort study has been designed according to the IDEAL 2b framework for the evaluation of surgical interventions. Stage 2b, refers to the exploration stage in evaluating new surgical techniques and this will be with regard to the development of deroofing as an intervention for HS in the UK. We will work closely with HISTORIC to define outcome measurement instruments to assess treatment response and will provide estimates of Minimal Important Difference (MID) for each.

Recommendations for future primary research will be formulated in a consensus workshop attended by study participants, clinicians and researchers.

In addition, our proposal includes a nested qualitative study that will further characterise the interventions used in the cohort study and help to understand patients' and clinicians' perspectives in making informed treatment choices. Its objectives are to (i) characterise and document best practice in delivering the study interventions, (ii) understand barriers and facilitators to recruit into future HS randomised controlled trials (RCTs), and (iii) understand patients' perspectives on treatment choices.

Particular focus will be given to characterising the surgical and laser interventions, and training videos will be produced to inform development of suitable training packages for use in future RCTs. The videos are part of laying the groundwork for quality assurance in a phase III study, following the IDEAL Stage 2b approach (http://www.ideal-collaboration.net/about-ideal/exploration/).

#### 4.1 Rationale for current study/Justification of treatment options

Informed by the requirements of the National Institute for Health Research Health Technology Assessment (NIHR HTA) Commissioned Funding Call, the THESEUS study includes: (i) a non-randomised, non-CTIMP prospective cohort study with 12-months' follow-up, supported by a bespoke and repeatable training package; (ii) nested mixed methods and process evaluation studies; and (iii) a consensus workshop to agree key design features of future RCTs of HS treatments.

The cohort study has been designed according to the IDEAL 2b framework for the evaluation of surgical interventions. The IDEAL framework outlines a process of 'innovation, development, exploration, assessment, and long-term study' (8). Stage 2b, refers to the exploration stage in evaluating new surgical techniques.

Our research plan is informed by surveys sent to HS patients (n=358), dermatologists (n=57) and plastic and general surgeons (n=225). The UK dermatologists survey is an update of a previous version published in 2015 (9).

PROSPECTIVE COHORT STUDY (0 to 36 months)

Health Technologies being assessed:

- (i) oral doxycycline 200mg OD (this is likely to be a standard care comparator for many future RCTs);
- (ii) oral clindamycin and rifampicin both 300mg BD as a combined course for 10 weeks (commonly used second-line intervention, when first-line oral therapy has failed);

- (iii) laser treatment (recommended in the European HS Guidelines but not widely used for HS in the UK) (3);
- (iv) deroofing of sinus tracts (again recommended in the European Guidelines but very uncommon in the UK) (3, 10);
- (v) conventional surgery (narrow or wide excision, with a range of closure methods).

Choice and dose of study interventions has been informed by results of our stakeholder surveys. Oral doxycycline and clindamycin solution are standard treatments, as well as the combination of oral rifampicin and clindamycin for 10-12 weeks. However, there is a great deal of variation in both surgical and medical approaches.

Hair-removal laser treatment and deroofing of sinus tracts are not standard treatments in the UK, but they are both included in the summary recommendations of the European Dermatology Forum HS guidelines (3).

Hair removal is performed by individuals trained and certified in the use of medical lasers (clinicians or NVQ level 3 certified individuals), and it is believed that only limited use in people with HS in the UK may be due to underuse of referral pathways to allow patients to access laser treatment. Training in laser treatment is already formalised as part of medical laser training. Certification is required for individuals to be insurable. Providing formal training in laser treatment within this project is not necessary, however a laser protocol will be provided.

Deroofing uses standard surgical equipment and transferable skills that will already be possessed by surgeons and some dermatologists (10). However, there is limited awareness of the technique in the UK, which is likely to account for its low uptake.

Each study site will offer at least 4 of the 5 interventions.

# 5 Study objectives/endpoints and outcome measures

#### 5.1 Primary objectives

To inform the design of future HS RCTs and to understand how HS treatments are currently used.

#### 5.2 Secondary objectives

To determine:

- i) feasibility of recruitment for future RCTs of HS treatments;
- ii) choice and characterisation of study interventions (dose of medication, type of surgical techniques used);
- iii) current patient pathways and understanding of what influences patients' and clinicians' treatment choices;
- iv) choice, feasibility and responsiveness of outcome measure instruments, including evaluation of minimum important difference (MID) to inform sample size calculations; and
- v) consensus-agreed recommendations for future study designs.

#### 5.3 Primary outcomes measure(s)

Proportion of participants who are eligible, and hypothetically willing, to use the different treatment options.

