#### 9.3 Recruitment rates

A total of 150 participants will be recruited at an expected rate of 1-2 per month per site.

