#### 11.1 Assessments / Data collection

The schedule of assessments is summarized in figure 1. A window of 2 weeks is permissible either side of the intended follow up date. Safety blood tests (full blood count, renal function, liver function) will be required at baseline and after 4 weeks only for participants choosing the clindamycin and rifampicin intervention. These blood tests are part of usual care and will be carried out within the hospital setting. The participants treating clinician within secondary care will review the blood results and inform the participant whether they can start/continue with their chosen clindamycin and rifampicin intervention.

Efficacy outcome measures will include the six core domains recommended by the HISTORIC core outcome set initiative for HS: (i) Pain (using a numeric rating scale) (ii) HS-specific quality of life (HiSQOL), (iii) global assessment, (iv) progression of course (flare frequency), (v) physical signs and (vi) symptoms (drainage resulting in need for dressings and fatigue) (7). HISTORIC-recommended instruments will be employed where these are available, plus a generic measure of quality of life (EQ-5D). We will report completeness of each outcome at each time point.

Pain NRS will be measured at the baseline appointment and then on a daily basis for the first 12 weeks following treatment commencement via mobile telephone text message.

Figure 1. Schedule of interventions and assessments

Review number	-1	0	1	2	3	4
Planned month	-1	Baseline	3	6	9	12
Screening logs	Х	Х				
Eligibility assessment	Х	Х				
Demographics and consent		Х				
Clinical examination including Hurley stage		Х	Х	Х	Х	Х
Interventions for which participant is potentially eligible		Х				
Intervention received, with reasons for choice (including treatments switched after baseline)		X	Х	Х	Х	Х
Outcomes						
HS quality of life questionnaire (HiSQOL)		Х	Х	Х	Х	Х

Dermatology Life Quality Index (DLQI)	Х	Х	Х	Χ	X	
EQ5D-5L questionnaire	Х	Х	Х	Х	Х	
Pain visual analogue scale (VAS/NRS)	Х	Х	Х	Х	Х	
Pain score (via text message)	12 we	12 weeks from start of intervention				
Need for dressings	Х	Х	Х	Х	Х	
Fatigue questionnaire	Х	Х	Х	Х	Х	
Patient global assessment	Х	Х	Х	Х	Х	
Anchor question for change in severity		Х	Х	Х	Х	
Flares	Х	Х	Х	Х	Х	
Assessment of HS physical signs	Х	Х	Х	Х	Х	
Adverse effects of study treatment		Х	Х	Х	Х	
Treatment fidelity		Х	Х	Х	Х	
End of study questionnaire (participants and clinicians)					Х	

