#### 13.1.2 STUDY 2 - Stakeholder perspectives on HS treatment and research (an interview study)

SAMPLE. Our PPI consultation has reinforced the value of talking to stakeholders about the treatment of HS, stressing the complex journeys of diagnosis and treatment that many experience.

Approximately one-third of cohort participants (up to 50 participants) and one clinician per recruiting site (n=10) will be invited to participate in semi-structured interviews. A member of the research team will contact participants to arrange a time to interview them, over the telephone. Due to the COVID-19 pandemic, participants will not have the option for a face-face interview.

Purposive sampling of cohort participants will ensure that more patients exposed to invasive procedures (conventional surgery, de-roofing, and laser treatments) will be interviewed than those exposed to medical management (30/20). Sampling will also ensure variation in age, gender, ethnicity, HS severity and geographic location.

Each recruiting centre will nominate one clinician for inclusion in this study, ensuring a balance of dermatology and surgical colleagues.

DATA COLLECTION. Telephone interviews with participants will take place throughout the cohort study and engage with them at different points in their involvement. Interviews will focus upon their choice of treatment and factors informing this; their experience of the study treatment(s); their satisfaction with treatment; hypothetical willingness to be randomised into a future RCT and, their experience of research processes. Our PPI contributors have warned that a more discursive

consideration of HS and its impact may not be appropriate here, potentially introducing sensitive or emotional issues that are not directly relevant to aims and objectives of this research.

Interviews with clinicians will focus upon their management of HS; service delivery issues associated with different treatment options; willingness to randomise to the different treatment options; and recommendations for future HS clinical studies.

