#### 15 Statistical considerations

#### 15.1 Sample size

With a sample size of 150, we will be able to estimate the proportion of participants who are hypothetically willing and eligible to be randomised in a clinical study to within a 95% confidence interval of  $\pm$  7%. We also wish to identify the case-mix of patients for each of the possible treatment options. From our patient survey, the least favourable treatment option (with 13%) was minor surgical operations, which would include deroofing of sinus tracts. 150 patients will provide us with 20 patients

opting for this non-medical intervention, which is sufficient to explore delivery in the IDEAL 2b evaluation.

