# 16 Analysis

#### 16.1 Main analysis

We will describe the willingness of patients to be recruited overall and by patient intervention stated preferences and treatment uptake, including estimating intra-cluster correlation coefficients to explore clustering by centre. The group membership of each intervention will be described using descriptive statistics using data collected at baseline (month 0) (including demographics, clinical examination). Over the study period, we will report whether patients continue with and adhere to

their chosen intervention or whether they switch to alternative HS interventions during the study period. Treatment fidelity will be defined differently for each intervention option (e.g. oral clindamycin and rifampicin both 300mg twice daily for 10 weeks vs a one off surgical intervention) and will be described over the follow-up period. Within an intervention option, and where there is variation in fidelity, we will explore the possible predictors using regression modelling.

Where a patient switches intervention, we will report the reasons for this and again explore the possible predictors of switching (including intervention type, site, and other baseline demographics). Rates of loss to follow-up over the study period will be reported and we will examine whether there are any particular characteristics associated with response at 6 months.

Average change over time will be estimated for each efficacy outcome for each group with 95% confidence intervals. We will estimate the clustering/variability between surgeons/treating clinicians. Potential confounders of outcome will be assessed using regression methods.

Global assessment will be used as our anchor tool to allow estimation of MID. This will be used to dichotomise outcomes into those with clinically meaningful change and those without clinically meaningful change (stable or worse). Receiver operating characteristic curves will be generated, and the area under the curve (AUC) calculated as a measure of the outcome's ability to detect clinically relevant change. Youden's J index will be used to determine the minimal important change (MIC), and the MID will be calculated as the difference between the mean change in the improved and stable subgroups (17).

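### The primary outcome (willing to use a treatment), the precision statement (willing to be randomised) and the main analysis (willing to be recruited) name different quantities, and the schedule names no willingness item for all participants

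*Protocol*

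**What the plan says.** **Primary outcome.** Section 5.3 and the synopsis give "Proportion of participants who are eligible, and hypothetically willing, to use the different treatment options". This asks about accepting a treatment, and it implies a separate proportion for each of the five interventions.

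**Precision.** Section 15.1 says that 150 participants allow estimation of the proportion "hypothetically willing and eligible to be randomised in a clinical study to within a 95% confidence interval of" ±7%. This is a single proportion and concerns accepting random allocation. The assumed true proportion is not given.

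**Analysis.** Section 16.1 begins: "We will describe the willingness of patients to be recruited overall". It adds a breakdown by stated preference and by uptake. It does not mention willingness to use each option.

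**Data collection.** Figure 1 (Section 11.1) has a baseline row, "Interventions for which participant is potentially eligible", and a row at every visit for the intervention received and the reasons for choosing it. No row names willingness to use or to be randomised. The participant interviews in Section 13.1.2 cover "hypothetical willingness to be randomised into a future RCT and, their experience of research processes". They are optional (Section 9.4), limited to 50 people and purposively sampled, 30 from invasive and 20 from medical treatment. Section 13.1.3 adds free-text questions for all participants at 12 months on satisfaction, treatment choice, and barriers and facilitators to research.

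**The concern.** Willingness to use a treatment and willingness to be randomised to it are different things. A patient may accept both antibiotics and surgery yet refuse to let chance decide between them. The first proportion measures acceptability. Only the second bears directly on how many patients a future RCT could recruit. The lay summary itself separates joining a future study from preferring a treatment, and Section 5.2 lists feasibility of RCT recruitment as a secondary objective.

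The study has one primary outcome, and its purpose is to inform the design of later trials. If acceptability is reported as though it were willingness to be randomised, recruitment forecasts for those trials could be misled. If sites follow the schedule without a named question, the willingness half of the primary outcome may not be recorded in a usable form for everyone.

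**Working it through.** **1. The definitions side by side**

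| Place | Quantity | Number of proportions | Precision stated |
|---|---|---|---|
| 5.3 and synopsis | eligible and willing to use | one per option | none |
| 15.1 | eligible and willing to be randomised | one | ±7% |
| 16.1 | willing to be recruited | overall, and by preference and uptake | none |

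The other justification in 15.1 is that the least favoured option drew 13% in the patient survey: 0.13 × 150 = 19.5, which reproduces the stated 20. It concerns the number choosing an option, which is a secondary outcome in 5.4. It gives no precision for the primary outcome either.

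**2. Can the scheduled rows supply willingness to use?**

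The eligibility half is scheduled at baseline. The row for the intervention received does not supply the other half. Under Section 9.5.1 each participant chooses one of the five interventions, so willingness to use the options not chosen is unobserved. Under Section 6, a person who prefers a treatment outside those the site offers is not recruited, so nearly every participant accepts at least one option by design. The information sought lies in the options not chosen.

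**3. The plan's ±7%**

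Inputs: n = 150 ("A total of 150 participants will be recruited at an expected rate of 1-2 per month per site", Section 9.3); 95% confidence; p not stated, so it is varied. Half-width = 1.96 × √(p(1−p)/n).

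- p = 0.5: 1.96 × √(0.25/150) = 8.0 points
- p = 0.3: 1.96 × √(0.21/150) = 7.3 points
- p = 0.25 or 0.75: 1.96 × √(0.1875/150) = 6.9 points

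Setting the half-width to 0.07 gives p(1−p) = 0.07² × 150 / 1.96² = 0.191, so ±7.0 points is met for p up to about 0.258 or from about 0.742. The sample size needed for ±7 is 1.96² × p(1−p)/0.07², which is 147 at p = 0.25 and 196 at p = 0.5. The stated figure can therefore be reproduced near 25% or 75%, but not at the conservative value of 50%.

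The formula depends only on n and p. With 150 complete answers, willingness to use and willingness to be randomised are estimated equally well.

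**4. The places where willingness might otherwise come from**

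- Interviews, n = 50: 1.96 × √(0.25/50) = 13.9 points at p = 0.5, and 1.96 × √(0.1875/50) = 12.0 at p = 0.25 or 0.75. The 30/20 split is set by design, so an unweighted proportion need not match the cohort.
- 12-month questionnaire: answers come after treatment and after loss to follow-up. With losses of 10%, 20% and 30% (assumed; the protocol gives none), n is 135, 120 and 105, and the half-width at p = 0.5 is 8.4, 8.9 and 9.6 points.

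**The case against.** **No item named is not the same as no item collected.** Figure 1 lists assessments rather than questions, and the case report forms and SAP are not shown. A willingness question could sit in the baseline eligibility form or in the end-of-study questionnaire, and the reference to stated preferences in 16.1 hints that something of the kind exists. This stands. A reader might infer that willingness is not collected at all; the protocol shows only that no item and time point are named for all participants.

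**The sample size is not at fault.** A reader might infer that 150 participants cannot answer the primary question. Step 3 shows otherwise: either quantity is estimated to about ±7 to ±8 points for p between 0.25 and 0.75.

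**The interviews have a qualitative role.** They are assigned to framework analysis, and nothing says they supply the ±7% estimate. Purposive sampling suits that role, so ±13.9 is not a failed promise. It shows only that the one place where participants' willingness to be randomised is named could not serve as the source. The size of any bias from the 30/20 split cannot be derived, because the protocol gives no willingness rates.

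**Perhaps there are two quantities rather than three.** Willingness to be recruited can be read with the RCT-recruitment objective in 5.2, and so with 15.1. That is a fair reading, but it leaves the main analysis describing the feasibility quantity while the declared primary outcome is not analysed in its own terms.

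**This could be left to the SAP.** A SAP can refine an estimator. The protocol, however, already fixes conflicting definitions of its only primary outcome, and a SAP cannot create answers that were not collected.

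**Conclusion.** The concern holds as an internal inconsistency with a gap in traceability. The protocol declares willingness to use as primary, states precision for willingness to be randomised, and analyses willingness to be recruited. Its schedule does not say where willingness is measured in all participants. The declared primary outcome has no stated precision, and the ±7% has no stated assumed proportion: at n = 150 the half-width is 8.0 points at p = 0.5 and 6.9 at p = 0.25 or 0.75.

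These figures assume complete answers from all 150, simple binomial sampling without clustering by centre, and a denominator of all participants. A proportion taken only among those eligible for an option would be less precise. The finding should be settled because it concerns the only primary outcome, and a short baseline question changes what the study can conclude.

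**What to change.** - State in 5.3, 15.1 and 16.1, and in the synopsis, that the primary outcome is the proportion eligible for and willing to use each option. Declare the proportion eligible and willing to be randomised as a separate, named RCT-feasibility outcome.
- Add two yes/no items to the Figure 1 baseline visit for all 150 participants, asked for each intervention for which the participant is eligible: willing to use it, and willing to be randomised in a trial that includes it. Baseline precedes both treatment and loss to follow-up.
- Use the interviews only to explain the answers.
- Restate the precision in 15.1 for each proportion with its assumed value, for example ±8.0 points at p = 0.5 and ±6.9 at p = 0.25 or 0.75.

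Cost: at most 2 × 5 = 10 extra tick-box answers per participant at baseline, aligned wording in the sections named, and a slightly less favourable stated precision if the conservative value of p is used.
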